3.1.4 Part 2 – Arms 2A-2B

Figure 3-3 Part 2 Design

Approximately 45 patients who meet the inclusion criteria will be randomized in a 2:1 fashion within 24 hours pre-transplant to receive one of the 2 treatment arms (Figure 3-3):

1. **Arm 2A**, n=30: Basiliximab 20 mg (Days 1, 4) + **CFZ533 at 10 mg/kg IV** (17 doses) + MMF 1.0g BID + CS
2. **Arm 2B Control/SoC**, n=15: Basiliximab 20 mg (Days 1, 4) + Tac (4-11 ng/mL) + MMF 1.0 g BID + CS

Induction therapy must be started within 2 hours prior to transplantation, or according to local practice.

The first dose of CFZ533 will be administered IV pre-transplant or intra-operatively. Drug administration will begin after randomization and must be completed by the time of unclamping. Subsequent doses of CFZ533 will be administered IV (Arm 2A), over a period of 12 months.

Other study drugs (apart from Basiliximab) should be started within 24 hours post-transplant. The second dose of basiliximab will be administered on Day 4, or according to local practice.

The day of randomization and transplant will be considered to be study Day 1. Further treatment will be given on study Days 3, 7, 15, 29, 43, 57 and then monthly thereafter until Months 12 (up to approximately Day 337). Subjects will then undergo Study Completion evaluations.

The primary endpoint of Part 2 will be assessed to determine whether the success criteria (safety and tBPAR) have been met

Corporate Confidential Information

Corporate Confidential Information

If notable AEs or safety concerns meeting the *a priori*-defined stopping criteria (see [Section 5.5.10](#)) one of the planned dose levels may be changed or discontinued via amendment.

Subjects will undergo Study Completion evaluations at the end of the trial.

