Patients will be regularly evaluated while domiciled and upon return to the clinic for signs and symptoms which might indicate a severe infection, i.e., fever, nausea, myalgia, headache, arthralgia, chills, diarrhea, stiff neck, and malaise, and treated as appropriate per local practice depending on the infectious agent. Patients will be informed to report any of the aforementioned symptoms to the clinical staff to assure proper assessment and care can be administered in a timely manner.

Viral reactivation will be assessed for EBV, CMV and BK according to local practice on a regular basis.

Corporate Confidential Information

In agreement with the secondary objectives, changes in renal function will be assessed via serum creatinine and calculated creatinine clearance (MDRD).

Corporate Confidential Information

Hypercoagulability and coagulopathy will be assessed using standard coagulation studies, including prothrombin time (PT) and activated partial thromboplastin time (aPTT) according to local practice.

Finally, key safety data will be reviewed by the Sponsor in a blinded manner in an ongoing basis. A DMC will review un-blinded study data regularly and on an *ad hoc* basis to assess whether the benefit/risk of each treatment arm remains acceptable. *A priori* defined stopping criteria and guidelines ([Section 5.5.10](#)) in addition to the clinical opinion of the Investigator and biopsy results managed per local practice will be used to protect individual patient safety during the trial.

Corporate Confidential Information

Cases of serious infections or neoplasms will also be monitored and reviewed on an ongoing basis.

Based on the information outlined above, the risk of administering CFZ533 in combination with MMF, corticosteroids, and basiliximab as well as add on to a Tac-based standard of care regimen appears manageable and reasonable to investigating the clinical activity of CFZ533 in the intended patient population.

4 Population

Parts 1 and 2 (initial PoC phase) of this multicenter study will be conducted in approximately 20 centers worldwide. The study population of Parts 1 and 2 will consist of approximately 51 male and female *de novo* adult renal transplant patients.

The Investigator must ensure that all subjects being considered for the study meet the following eligibility criteria. No additional criteria should be applied by the Investigator, in order that the study population will be representative of all eligible subjects.

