5.5.13 Replacement of early withdrawals or discontinuations

The sponsor allows for over-recruitment of 2 patients in Part 1 and additional 10% in Part 2, to compensate for potential early withdrawals or discontinuations from the study.

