9.5.3.1 Main safety endpoint: estimated GFR using the MDRD formula

The key secondary and safety variable is renal function as assessed by eGFR (MDRD formula). This will be evaluated at Month 12 by comparing the mean eGFR values between groups.

The MDRD formula is defined as follows ([Levey et al 2003](#)):

$$\text{GFR } [\text{mL/min}/1.73\text{m}^2] = 186.3 * (\text{C}^{-1.154}) * (\text{A}^{-0.203}) * \text{G} * \text{R}$$

C is the serum concentration of creatinine [mg/dL]

A is age [years]

G=0.742 when gender is **female**, otherwise G=1

R=1.21 when race is **black**, otherwise R=1.

Local laboratory serum creatinine values will be used for all renal function data analysis. Serum creatinine results are in units of umol/L, so the following formula should be used to convert to the required unit of mg/dL:

$$\text{C}[\text{mg/dL}] = \text{serum concentration of creatinine } [\text{umol/L}] / 88.4.$$

Estimated GFR will be determined and summarized in each part of the study.

Handling of missing values/censoring/discontinuations

The analysis will be made on the FAS population. The following imputation method will be applied for patients with missing eGFR values:

- Patients that lose their graft will be assigned a value of zero for their missing GFR value.
- Patients that die or are lost to follow-up with a functioning graft will have an imputed value using the last-observation-carried-forward (LOCF) method.
- For patients that discontinue randomized treatment the eGFR will be considered missing after applying the windows defined in [Section 9.4.1](#).

Graft loss patients do not have a functioning graft; hence the lowest possible GFR value (zero) will be assigned to such patients. In contrast, patients that die with a functioning graft, die for different reasons (e.g., suicide, car accident, cancer). Similarly, patients who are lost to follow-up have renal function, but missing values for various reasons (e.g., moving from the area or not being able to make the site visit during the Month 6 or Month 12 visit window). Patients who have a functioning graft at the time of death or are Lost to Follow-up with a functioning graft will be analyzed via an imputation method that employs LOCF.

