These calculations assume that the primary efficacy variable, rate of tBPAR, follows a binomial distribution. The prior distribution for the control tBPAR rate, Beta(1, 13), is estimated from a Bayesian meta-analysis of tBPAR rates from four previous studies using a control treatment similar to the one used in this study. The four studies were selected from the studies used in a previous Novartis generated meta-analysis studies and are summarized in Table 9-1.

Table 9-1 Summary of historical control data

Study	Treatment	Number of patients with tBPAR	Total number of patients	tBPAR rate
1 - Vincenti et al 2007	B+Tac+MMF+CS	24	346	0.069
2 - Silva et al 2007	B+Tac XL+MMF+CS	17	214	0.079
3 - Silva et al 2007	B+Tac+MMF+CS	8	212	0.038
4 - Scholten et al 2006	B+Tac+ MMF(0.5g)+CS	4	63	0.063

B=basiliximab

Prediction of the control rate for a future trial resulting from the Bayesian meta-analysis is shown in Figure 9-3.

Figure 9-3 Results of Bayesian meta-analysis prediction

[figure not shown]

Figure 9-3 shows estimates of response rate and 95% credible intervals for each study based on study data alone (dashed lines) and from the meta-analysis (solid lines). The overall prediction for response rate in a future study is shown in red together with the mean and 95% credible interval from the posterior distributions and n^* , the prior number of observations that these data would contribute to a future analysis.

To allow for a simple randomization ratio for allocation of patients to treatment groups, it was decided to reduce the control arm to 15 patients, compared to 30 for the CFZ533 arms. Thus a prior beta distribution of Beta (1, 13) was chosen, which has a mean value of 7 with 95% CI (0.2, 24) and an approximate weight of 14 patients.

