9.7 Power for analysis of key secondary variables

Table 9-2 provides 80% and 95% CIs for between-treatment difference (CFZ533-control regimen) based on an assumed SD and difference for eGFR_{MDRD}. Since this is an exploratory phase 2 trial, evidence of renal benefit will be based on a 80% CI. In line with the SYMPHONY study (Ekberg et al 2007), a difference of 6.5 mL/min/1.73m² between treatment regimens is considered to be the lower limit of clinically relevant benefit.

Table 9-2 Two-sided 80 and 95 percent example CIs for between-treatment difference (CFZ533-Control regimen) of calculated eGFR (MDRD), assuming dropout rate = 30 percent (n = 53/group)

Observed Standard Deviation	Observed difference in eGFR _{MDRD} CFZ533 – control	80% CI	95% CI
16	4.0	(-0.0, 8.0)	(-2.2, 10.2)
	5.0	(1.0, 9.0)	(-1.2, 11.2)
	6.0	(2.0, 10.0)	(-0.2, 12.2)
	7.0	(3.0, 11.0)	(0.8, 13.2)
	8.0	(4.0, 12.0)	(1.8, 14.2)
18	4.0	(-0.5, 8.5)	(-3.0, 11.0)
	5.0	(0.5, 9.5)	(-2.0, 12.0)
	6.0	(1.5, 10.5)	(-1.0, 13.0)
	7.0	(2.5, 11.5)	(0.0, 14.0)
	8.0	(3.5, 12.5)	(1.0, 15.0)
20	4.0	(-1.0, 9.0)	(-3.7, 11.7)
	5.0	(-0.0, 10.0)	(-2.7, 12.7)
	6.0	(1.0, 11.0)	(-1.7, 13.7)
	7.0	(2.0, 12.0)	(-0.7, 14.7)
	8.0	(3.0, 13.0)	(0.3, 15.7)

10 Ethical considerations

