Data for CFZ533 administration and concomitant therapies will be listed by treatment group and patient. The duration (days) of CFZ533 study medication administration will be summarized and listed. The duration will be calculated by subtracting the date of the last administration of study medication from the date of first administration and then adding the dosing interval for CFZ533. In calculating the duration of treatment, days of temporary interruption of study medication for any reason will be included, i.e, any days of interruptions will not be excluded from the duration of treatment. Further, the frequency of dose changes (including temporary dose interruption) will be presented by reason for the change.

Average daily doses of each treatment will be presented in a summary table and will be listed by treatment and patient. “Zero” will be used for periods of temporary interruption of study medication for any reason.

The number and percentage of patients who prematurely discontinued study medication will be summarized by reason for discontinuation.

If the number of events allow, Kaplan-Meier (KM) estimates of time to discontinuation of study medication curve will be constructed and presented graphically. In this analysis, patients

who have not discontinued study medication will be censored with the censoring time as defined by the last contact day.

Concomitant immunosuppressants

The dose of administered Basiliximab, MMF, Tac and CS will be listed by treatment and patient.

The dose of antibodies used for the treatment of acute rejection episodes will be summarized by treatment and listed by treatment and patient.

Other co-medications

Concomitant medications, other than immunosuppressants and CS mentioned above, will be listed by patient and summarized by therapeutic class and preferred term by presenting the number and percentage of patients using each medication for each treatment group.

Calculated eGFR

The main safety endpoint is calculated eGFR.

Patients will be considered as “on treatment”, whilst they are taking their assigned randomized treatment. If a patient switches to an alternative treatment or stops taking their assigned randomized treatment, this data will be excluded from the summaries, figures and analysis for eGFR data.

Calculated eGFR as determined by the central lab will be summarized by visit. The calculated eGFR will be presented graphically to show the overlaid patient profiles and mean profile over time.

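### The eGFR precision table assumes 53 patients per group, but Part 2 randomises 30 and 15, so the printed intervals are about 50–61% of the width this design gives

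*Protocol*

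**What the plan says.** Protocol 9.5.3.1 gives eGFR a leading place: "The key secondary and safety variable is renal function as assessed by eGFR (MDRD formula"). Section 9.7 says that "evidence of renal benefit will be based on a 80% CI" and takes 6.5 mL/min/1.73 m² as the smallest clinically relevant difference. It then supplies Table 9-2, with example 80% and 95% intervals for SDs of 16, 18 and 20 and observed differences of 4 to 8, under the caption "assuming dropout rate = 30 percent (n = 53/group").

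The design sections give other numbers:

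- Section 3.1.4: "Approximately 45 patients who meet the inclusion criteria will be randomized in a 2:1 fashion within 24 hours pre-transplant", with 30 in Arm 2A and 15 in Arm 2B.
- Section 9.6: "it was decided to reduce the control arm to 15 patients, compared to 30 for the CFZ533 arms".
- Section 4 (Population): "The study population of Parts 1 and 2 will consist of approximately 51 male and female" adult recipients.
- Section 5.5.13: "The sponsor allows for over-recruitment of 2 patients in Part 1 and additional 10% in Part 2".

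On missing eGFR, Protocol 9.5.3.1 and SAP 7.1.2 impute zero after graft loss and carry the last value forward after death or loss to follow-up with a functioning graft. Values after a patient stops or switches randomised treatment are not used. SAP 7.1.2 says that "this data will be excluded from the summaries, figures and analysis for eGFR data".

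SAP 7.1.2 specifies 90% intervals for the treatment difference from its mixed model. The visible SAP text does not mention the 80% interval.

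**The concern.** Table 9-2 is the only visible statement of how precisely the trial can estimate its key secondary variable. Its caption describes about twice as many evaluable patients as the whole study enrols (106 against about 51), split equally instead of 2:1. No visible text says that the table belongs to another design.

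A reader of Section 9.7 would conclude that an observed benefit at the 6.5 relevance limit gives an 80% interval clear of zero. If the real design cannot do that, the protocol overstates what Part 2 can show about renal function, which is half of its stated purpose (similar rejection rates with better renal function).

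**Working it through.** **Inputs.** SDs 16, 18, 20; differences 4 to 8; 30% dropout; 53 per group; relevance limit 6.5 (all Protocol 9.7). Arm sizes 30 and 15 (3.1.4, 9.6). Over-recruitment 10% (5.5.13).

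**Formula.** Unadjusted two-sample interval: half-width = t(df = n1 + n2 − 2) × SD × √(1/n1 + 1/n2).

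**Step 1: reproduce the table.** 75 randomised per group × 0.7 = 52.5, which rounds to the caption's 53. With 52.5 per group:

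- √(2/52.5) = 0.195 and t(80%, 103 df) = 1.290. For SD 16 the half-width is 1.290 × 16 × 0.195 = 4.03.
- 80% half-widths: 4.03, 4.53, 5.03. 95% half-widths: 6.19, 6.97, 7.74.

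All 30 printed intervals are reproduced after rounding. With exactly 53 per group, only the SD 18, 95% column differs, by 0.1. The table was therefore calculated for about 53 per group, and the caption is not a typing slip. The implied total is 2 × 75 = 150 randomised.

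**Step 2: put in this trial's arms.** For 30 versus 15, √(1/30 + 1/15) = 0.316 and t(80%, 43 df) = 1.302. For SD 16 the half-width is 1.302 × 16 × 0.316 = 6.59. The other cases follow in the same way.

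| Evaluable | 80% half-width, SD 16 / 18 / 20 | 95% half-width, SD 16 / 18 / 20 | Printed 80% width as share |
|---|---|---|---|
| Table 9-2 (52.5 per group) | 4.03 / 4.53 / 5.03 | 6.19 / 6.97 / 7.74 | – |
| 33 vs 17 (full over-recruitment, no loss) | 6.21 / 6.98 / 7.76 | 9.60 / 10.81 / 12.01 | 65% |
| 30 vs 15 (no dropout) | 6.59 / 7.41 / 8.23 | 10.20 / 11.48 / 12.76 | 61% |
| 21 vs 10.5 (30% dropout) | 7.93 / 8.92 / 9.91 | 12.36 / 13.90 / 15.45 | 51% |

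Rounding the control arm down to 10 gives 80% half-widths of 8.06, 9.07 and 10.08 (50%).

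**Step 3: the protocol's own 6.5.** 80% interval at an observed difference of 6.5:

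| SD | 53 per group | 30 vs 15 |
|---|---|---|
| 16 | 2.5 to 10.5 | −0.1 to 13.1 |
| 18 | 2.0 to 11.0 | −0.9 to 13.9 |
| 20 | 1.5 to 11.5 | −1.7 to 14.7 |

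**Step 4: illustration under an assumed rule.** The protocol sets no pass threshold. If evidence of benefit is read as an 80% lower limit above zero, 11 of the 15 printed rows meet it. That falls to 3 of 15 at 30 versus 15, 1 of 15 at 21 versus 10.5, and none at 21 versus 10.

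At a true difference of 6.5, the chance of meeting the rule is Φ(6.5 / (SD × √(1/n1 + 1/n2)) − 1.28). For SDs of 16, 18 and 20:

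- 53 per group: 79%, 72%, 65%.
- 30 versus 15: 50%, 44%, 40%.
- 21 versus 10.5: 42%, 37%, 34%.

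The noncentral t distribution agrees within one percentage point.

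**The case against.** Several counter-arguments deserve weight.

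- **A leftover from a larger design.** Protocol 9.6 and the sample logs still mention a Part 3, and the SAP, written against an earlier protocol version, describes three parts. This may well explain the table. It is an inference, though: Section 9.7 presents the table as this trial's precision, and a leftover table still needs correcting.
- **The lower end is a scenario.** The 30% dropout comes from the same caption that does not fit, and no on-treatment retention rate is given for Part 2. Actual loss could be larger, smaller or unequal between arms. In the SAP's repeated-measures model, patients who stop still contribute earlier visits, so completer counts are not its effective sample size. This stands: 61% is the documented-n figure, and 50–51% is the table's own dropout assumption applied to the real arms.
- **The zero-crossing is marginal at SD 16.** At 30 versus 15 the lower limit is only −0.1, and at 33 versus 17 it becomes 0.3 (6.5 − 6.21). This also stands, but the printed width is still only 65% of the design's width in that most favourable case.
- **Exploratory trial, example intervals.** The SDs and differences are examples, but n is a fact of the design, and the same paragraph makes the 80% interval the basis for evidence of benefit.
- **The 80% and 90% levels may serve different analyses.** The time points named with the SAP model are the Month 3 and Month 6 interims, while Protocol 9.5.3.1 evaluates eGFR at Month 12. The point is minor and the conclusion does not depend on it.

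**Conclusion.** The concern holds. Table 9-2 states a precision that the 30 versus 15 design does not have. The printed widths are 61% of the design's with no dropout and 50–51% with the table's own 30% dropout. Full over-recruitment with no loss raises the share only to 65%.

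The widths are unadjusted two-sample t-intervals, as in the table. The SAP's covariate-adjusted mixed model could give different precision, but the documents do not quantify this. The row counts and success chances also need the assumed rule that the 80% lower limit exceeds zero.

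This should be fixed because it concerns the key secondary variable, but its reach is limited: neither the tBPAR success criterion nor the stopping rules use this table.

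**What to change.** In Protocol 9.7, recompute Table 9-2 for 30 versus 15 randomised, once with no dropout and once with 30% dropout (21 versus 10 or 11). Correct the n in the caption and label the dropout rate as an assumption. Simply deleting the table would leave eGFR with no visible precision statement.

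In SAP 7.1.2, add that the 80% interval named in Protocol 9.7 will be reported from the same model, beside the 90% interval.

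The cost is one table and one SAP sentence. The stated precision becomes less favourable. Patient numbers, endpoints and analysis sets do not change.

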10.1 Regulatory and ethical compliance

This clinical study was designed and shall be implemented and reported in accordance with the ICH Harmonized Tripartite Guidelines for Good Clinical Practice, with applicable local regulations (including European Directive 2001/20/EC, US Code of Federal Regulations Title 21, and Japanese Ministry of Health, Labor, and Welfare), and with the ethical principles laid down in the Declaration of Helsinki.

10.2 Informed consent procedures

Eligible subjects may only be included in the study after providing written (witnessed, where required by law or regulation), IRB/IEC-approved informed consent, or, if incapable of doing so, after such consent has been provided by a legally acceptable representative of the subject. In cases where the subject's representative gives consent, the subject should be informed about the study to the extent possible given his/her understanding. If the subject is capable of doing so, he/she should indicate assent by personally signing and dating the written informed consent document or a separate assent form. Informed consent must be obtained before conducting any study-specific procedures (i.e., all of the procedures described in the protocol). The process of obtaining informed consent should be documented in the subject source documents.

Novartis will provide to Investigators in a separate document a proposed informed consent form that complies with the ICH GCP guideline and regulatory requirements and is

considered appropriate for this study. Any changes to the proposed consent form suggested by the Investigator must be agreed to by Novartis before submission to the IRB/IEC, and a copy of the approved version must be provided to the Novartis monitor after IRB/IEC approval.

Women of child bearing potential should be informed that taking the study drug may involve unknown risks to the fetus if pregnancy were to occur during the study and agree that in order to participate in the study they must adhere to the contraception requirement for the duration of the study. If there is any question that the subject will not reliably comply, they should not be entered in the study.

Corporate Confidential Information

In the event that Novartis wants to perform testing on the samples that are not described in this protocol, additional Institutional Review Board and/or Ethics Committee approval will be obtained.

10.3 Responsibilities of the investigator and IRB/IEC

The protocol and the proposed informed consent form must be reviewed and approved by a properly constituted Institutional Review Board/Independent Ethics Committee/Research Ethics Board (IRB/IEC/REB) before study start. A signed and dated statement that the protocol and informed consent have been approved by the IRB/IEC/REB, must be given to Novartis before study initiation. Prior to study start, the Investigator is required to sign a protocol signature page confirming his/her agreement to conduct the study in accordance with these documents and all of the instructions and procedures found in this protocol and to give access to all relevant data and records to Novartis monitors, auditors, Novartis Clinical Quality Assurance representatives, designated agents of Novartis, IRBs/IECs/REBs, and regulatory authorities as required. If an inspection of the clinical site is requested by a regulatory authority, the Investigator must inform Novartis immediately that this request has been made.

10.4 Publication of study protocol and results

Novartis assures that the key design elements of this protocol will be posted in a publicly accessible database such as clinicaltrials.gov. In addition, upon study completion and finalization of the study report the results of this trial will be either submitted for publication and/or posted in a publicly accessible database of clinical trial results.

11 Protocol adherence

This protocol defines the study objectives, the study procedures and the data to be collected on study participants. Additional assessments required to ensure safety of subjects should be administered as deemed necessary on a case by case basis. Under no circumstances should an Investigator collect additional data or conduct any additional procedures for any research related purpose involving any investigational drugs.

Investigators ascertain they will apply due diligence to avoid protocol deviations. If the Investigator feels a protocol deviation would improve the conduct of the study this must be considered a protocol amendment, and unless such an amendment is agreed upon by Novartis and approved by the IRB/IEC/REB it cannot be implemented. All significant protocol deviations will be recorded and reported in the CSR.

